#### **4.3.7 Treatment Compliance and Drug Accountability**

Dose, site, visit, date, injection type and whether visit was attended and whether treatment was received will be recorded.

#### **4.3.8 Pharmacokinetics**

It is planned that a separate PK SAP will be developed to provide a detailed description of the PK analysis based on the Pharmacokinetic (PK) Analysis set. The current SAP will only present general information as per the study protocol. It should be noted that the Pharmacokinetic Analysis set presented in the current SAP is solely for general information purposes and will not be utilized for any analysis described in this document

---

Document:

C:\ProgramData\activePDF\Temp\DocConverter\API\Input\\$651f4dc0b253\$FE3041C5883446E892B20AB6D3F0E1BD.docx

Author: [name]

Version and Date: Version 1.0, 21 Apr 2023

Page 48 of 66

#### 4.3.8.1 Pharmacokinetic variables

Pharmacokinetic parameters will be generated using Phoenix WinNonlin Version 8.1 or higher for evaluation [1].

Data from participants who have sufficient concentrations to derive at least one PK parameter will be analysed. This analysis will include the parameters shown in **Error! Reference source not found..**

**Table 16 Pharmacokinetic Parameters**

PK parameter	Description	Unit
AUC0-t	Area under the concentration time-curve from time zero up to the last quantifiable concentration at time point t ( $C_t$ ), calculated using the linear up/log down trapezoidal rule.	ng*h/mL
AUC0-t1	Area under the concentration time-curve from time zero up to the concentration at time point t1 after which the concentrations start to rise again towards a second peak, calculated using the linear up/log down trapezoidal rule. t1 will be determined after review of the concentration-time profiles (immediate release component of total observed AUC).	ng*h/mL
AUCt1-t	Area under the concentration time-curve from time point t1 up to the concentration at time point t (slow release component of total observed AUC), calculated using the linear up/log down trapezoidal rule.	ng*h/mL
AUC0-∞	Area under the concentration time-curve from time zero up to infinity ( $∞$ ), calculated using the linear up/log down trapezoidal rule.	ng*h/mL
Cmax	Maximum plasma concentration	ng/mL
Cmax,0-t1	Maximum plasma concentration after administration from zero up to time point t1	ng/mL
Cmax,t1-t	Maximum plasma concentration after administration from time point t1 up to time point t	ng/mL
tmax	Time to reach $C_{max}$ after dosing	h
tmax,0-t1	Time to reach $C_{max,0-t1}$ after dosing	h
tmax,t1-t	Time to reach $C_{max,t1-t}$ after dosing	h
tlast	Time of the last quantifiable concentration	h
λz	Apparent terminal elimination rate constant	1/h
t½	Apparent terminal plasma half-life, calculated as: $\ln 2 / \lambda_z$	h

h= hours; PK= Pharmacokinetic

Document:

C:\ProgramData\activePDF\Temp\DocConverter\API\Input\\$651f4dc0b253\$FE3041C5883446E892B20AB6D3F0E1BD.docx

Author: [name]

Version and Date: Version 1.0, 21 Apr 2023

Page 49 of 66

Actual sampling times (relative to the IM injection of teverelix TFA at time zero) will be used for the calculation of all PK parameters, and all calculations will be made using non-rounded raw data. Where the actual sampling time is not recorded, the nominal sampling time will be used. Concentrations below the lower limit of quantification (LLOQ) will be taken as zero for calculation of concentration summary statistics and PK parameters.

A PK profile for a subject may be excluded from the PK analysis if the subject did not receive active treatment or had insufficient concentration data. Missing data will be excluded from the PK analysis. Removal of anomalous data (outliers) will be considered on an individual basis and reasons provided with an assessment of the impact on the study. Special consideration will be given to the estimation of  $\lambda_z$  and corresponding  $t_{1/2}$  values. Three or more points will be required within the terminal phase for  $\lambda_z$  and  $t_{1/2}$  to be estimated. The following additional variables will be tabulated to aid identification of potentially unreliable estimates of  $t_{1/2}$  and  $AUC_{0-\infty}$ :

#pts	the number of data points used in the calculation of $\lambda_z$ .
Rsq	the goodness of fit statistic for the terminal elimination phase. Note, if Rsq is less than 0.8, the $t_{1/2}$ will not be reported as the estimate will be classed as unreliable.
$\lambda_z$ _lower	the lower limit on time for values included in the calculation of $\lambda_z$ .
$\lambda_z$ _upper	the upper limit on time for values included in the calculation of $\lambda_z$ .
$\lambda_z$ _period	estimated as $(\lambda_z$ _upper - $\lambda_z$ _lower) / $t_{1/2}$ ; values < 2 would indicate that $\lambda_z$ and corresponding $t_{1/2}$ estimates are potentially unreliable Error! Reference source not found.
%AUC ext	the percentage of $AUC_{0-\infty}$ that is due to extrapolation from $C_t$ to infinity; values for $AUC_{0-\infty}$ will be classed as potentially unreliable if more than 20% of the total $AUC_{0-\infty}$ will be extrapolated Error! Reference source not found.

#### **4.3.8.2 Blood Sampling Time Points, Handling and Labelling of Blood Samples**

Blood samples for PK evaluation will be collected by venepuncture (or by using an indwelling catheter). A blood volume of 5 mL will be drawn per time point.

Blood is drawn for PK analysis according to the schedule in **Error! Reference source not found.** where time points are relative to IM injection of teverelix TFA at time zero, and the pre-dose PK sample is collected within 30 minutes prior to IM injection:

Handling and labelling of blood samples for PK analysis will be performed according to the instructions provided by the central analytical laboratory. Special tubes, labels, packaging, and instructions for storage and shipment will also be provided by the analytical laboratory. Blood samples should be shipped for analysis on the day of collection.

Blood teverelix TFA concentrations will be determined from all collected samples using a validated sensitive analytical procedure (e.g., inductively coupled plasma mass spectrometry) at a specialised central analytical laboratory.

After completion of all analyses, any leftover blood or blood samples will be destroyed immediately after termination of the study.

Stability data supports the storage of teverelix PK samples:

- In a freezer set at nominally -20°C for up to 376 days
- In a freezer set at nominally -80°C for up to 60 days

All PK parameters analysis will be described with details in a separate SAP.

---

Document:

C:\ProgramData\activePDF\Temp\DocConverter\API\Input\\$651f4dc0b253\$FE3041C5883446E892B20AB6D3F0E1BD.docx

Author: [name]

Version and Date: Version 1.0, 21 Apr 2023

Page 50 of 66

Table 17 presents the pharmacokinetic timepoints at which the blood samples will be collected.

**Table 17 Pharmacokinetic Timepoints**

Timepoint	Pre-dose	1 h	1.5 h	2 h	2.5 h	3 h	4 h	8 h	12 h	18 h	24 h a	48 h	72 h
Window	±0 day	±15 min	±15 min	±15 min	±15 min	±15 min	±15 min	±15 min	±15 min	±15 min	±15 min	±1 hour	±1 hour
	○	○	○	○	○	○	○	○	○	○	○	○	○
Timepoint	Day 4b	Day 7b	Day 10b	Day 12b	Day 14b	Day 21b	Day 28c	Day 35	Thereafter at each dosing visit and follow up visitd				
Window	±0 day	±0 day	±1 day	±1 day	±1 day	±1 day	±3 days	±3 days	±3 days				
	○	○	○	○	○	○	○	○	○				

PK=pharmacokinetic

a Participants will remain in the clinic as in-participants until after the 24-hour PK blood sample has been drawn after which time they will be discharged.

b From Day 4 onwards, when a PK sample is to be drawn on a non-dosing day, the PK sample should be drawn at the same time of day as the Day 0 pre-dose PK sample was drawn (+ 1 hour).

c Before dosing (up to 30 minutes pre-dose). Dosing should be done at the same time of day throughout the study (or at least + 1 hour of this timepoint).

d Including Day 203 to Final Assessment visits for Group 2 subjects

Document:

C:\ProgramData\activePDF\Temp\DocConverter\API\Input\\$651f4dc0b253\$FE3041C5883446E892B20AB6D3F0E1BD.docx

Author: [name]

Version and Date: Version 1.0, 21 Apr 2023

Page 51 of 66

#### 4.3.9 Pharmacodynamics

The following parameters will be investigated:

- T
- LH
- FSH
- PSA or hs PSA

Table 18 **Pharmacodynamic Blood Sampling Schedule** presents the PD blood sampling schedule for the study.

**Table 18 Pharmacodynamic Blood Sampling Schedule**

	Day 0 (pre-dose)	24h	48h	72h	Day 4	Day 7	Day 10
T (local)							
T (central)	○	○	○	○	○	○	○
LH	○	○	○	○	○	○	○
FSH	○	○	○	○	○	○	○
PSA	○					○	

	Day 12	Day 14	Day 21 b	Day 28	Day 35 c	Thereafter 7 days prior to each dosing visit	Thereafter at each dosing visit and follow up visit d
T (local)			○		○	○	
T (central)	○	○	○	○	○		○
LH	○	○	○	○	○		○
FSH	○	○	○	○	○		○
PSA		○	○	○	○		○

FSH=follicle stimulating hormone; hs=high-sensitivity; LH=luteinising hormone; PD=pharmacodynamic;

PK=pharmacokinetic; PSA=prostate-specific antigen; T=testosterone

a PD blood draws should be done at the same time of day as PK blood draws (pre-dose on Day 0)

b If PSA is <0.06 ng/mL hs PSA will be measured and reported. If PSA is ≥0.06 ng/mL then hs PSA will not be measured and reported.

c Group 1 only

d Including Day 203 to Final Assessment Visit for Group 2 subjects who enter Stage 3

Document:

C:\ProgramData\activePDF\Temp\DocConverter\API\Input\\$651f4dc0b253\$FE3041C5883446E892B20AB6D3F0E1BD.docx

Author: [name]

Version and Date: Version 1.0, 21 Apr 2023

Page 52 of 66

## 5. Statistical Methodology

### 5.1 General Statistical Methods

#### 5.1.1 General Information

All analysis data sets, and output will be produced by the Biostatistics Department of Quanticate Ltd using the SAS® system Version 9.4 or higher.

#### 5.1.2 Default Descriptive Statistics and Data Rules

In general, all continuous measures will be summarised descriptively, including number of available values, mean, standard deviation (SD), median, 1st quartile (for primary and secondary efficacy measures), 3rd quartile (for primary and secondary efficacy measures), minimum, maximum, and 95% confidence interval (CI) for the mean (for primary and secondary efficacy measures) if appropriate. Minimum and maximum values will be presented to the same decimal precision as the raw values, the 1st quartile, median, mean, 3rd quartile and 95% CI to one more, and the standard deviation, to two more decimal places than the raw values. Ordinal ratings may be handled as continuous data if appropriate.

Categorical data will be presented by frequency and percentage. All percentages will be presented to one decimal place except for values of 100%.

For AEs reported on a per-subject basis, medical history and concomitant medications, the denominator for the percentage calculation will be the number of subjects in each treatment arm. A subject will be considered at risk if the subject is in the Safety/FAS analysis set and entered the respective study period.

Unless otherwise specified, if reporting by visit, percentages are calculated using the number of subjects in the corresponding treatment group with non-missing data at that visit as the denominator, and if reporting overall, the denominator is the number of subjects in the given treatment group and population.

### 5.2 Hypotheses and Decision Rules

The approach for testing the hypothesis, if any, will solely rely on utilizing confidence intervals.

### 5.3 Handling of Missing Data

#### 5.3.1 Efficacy Endpoints

Missing efficacy data will not be replaced.

#### 5.3.2 Other Endpoints

##### 5.3.2.1 Laboratory Data

If a laboratory reports a concentration as unquantifiable (too low), they will set the value to 0. If a laboratory reports a concentration as unquantifiable (too high), they will set the value to the upper limit for that value. Values for samples that are not technically evaluable will be set to missing by the laboratory.

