7.2.1 Screening Examination (Day -6 to Day -1)

At the screening examination the following will be carried out and/or documented:

- Participant signs ICF as a part of the written participant information including the agreement concerning protection of personal data and direct access to source documents
- Date of visit
- Demographic data (height, weight, year of birth, age)
- Diagnosis of study indication (specify duration, severity as requested)
- Relevant medical history for the past 5 years
- Pre-treatment during the past 6 months
- Concomitant disease(s) (including date of diagnoses), concomitant therapy(ies)
- Physical examination (see Section 6.3.2)
- 12-Lead ECG (see Section 6.3.3)
- Safety laboratory tests (fasted \geq 8 hours)
- Total T (local laboratory)
- HbA1c
- Vital signs
- Check of inclusion and exclusion criteria

Concomitant diseases are to be documented, taking into consideration the medical history of the participant for the past 5 years. Findings that are not medically relevant for the study are: operation scars, accident scars, and bad sight etc.

7.2.2 Baseline Examination (Day 0), Stage 1

At baseline examination the following will be carried out and/or documented:

- Date of visit
- Weight, and BMI
- Documentation of changes in concomitant diseases and/or concomitant therapies (also medication taken only once and any non-prescription medicine)
- AEs (for definition see Section 6.2.4)
- Check of inclusion and exclusion criteria
- Physical examination
- 12-Lead ECG
- Continuous 24 h, 12-lead Holter ECG (Subset of 30 Group 2 subjects only)
- Safety laboratory tests (fasted (≥8 hours))
- Vital signs
- Pre-dose blood sampling for PK, PSA and PD analysis
- Pre-dose blood sampling for cardiac biomarkers (Group 2 only)
- Administration of the loading dose of teverelix TFA, which consists of IM followed by SC injection
- ISI
- Post-dose PK blood sampling

Additional Visits for Pharmacokinetic and Pharmacodynamic Samplings during Stage 1:

- During Stage 1, the participant will return to the study site for additional PK and PD blood sampling at 24, 48 and 72 hours post-dose, and on Days 4, 7, 10, 12, 14, and 21
- On Day 21 local testing of T levels will be performed
- On Days, 7, 14, and 21, blood sampling for PSA will be performed

7.2.3 Treatment (Maintenance Dose) Period Visits (Day 28 to Day 168), Stage 2

At the treatment period visits, the following examinations will be carried out and/or documented:

- Date of visit

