8.1.5 Analysis of Safety Data

Safety Endpoints

1. Number of participants with treatment-emergent AEs (defined as any AE occurring or worsening following treatment), summarised by system organ class (SOC) and preferred term (PT)

Note: Occurrence of ISRs will be included.

- 2. Mean changes in vital signs, triplicate 12-lead ECGs and laboratory data parameters at each visit during the 168-day treatment period, compared to baseline
- 3. Continuous 24 hour 12-lead Holter ECG (subset of 30 Group 2 subjects only)
- 4. Percentage of participants with ISRs at each visit during the 168-day treatment period *Note:* Photography of injections sites with visible injection site reactions will be performed at each visit, and ISRs will be scored based on a specific scoring matrix

The treatment-emergent AEs (defined as any AE occurring or worsening with the same date or later than that of the first application of study treatment) will be coded using the most recent version of the Medical Dictionary for Regulatory Activities (MedDRA) available at the study start date. This version will be used throughout the entire study. Updates to MedDRA will not be applied afterwards. Frequency tables for the preferred terms will be compiled based on participants experiencing an AE and on the number of AEs. These frequency tables will take the SOC into consideration.

All reported AEs will be listed and ISRs will be summarised.

The vital sign, triplicate 12-lead ECG, and laboratory data parameters will be presented using descriptive statistics and shift-tables with respect to normal ranges for each visit including changes from baseline.

Concomitant diseases and medical history will also be coded using MedDRA. These data will be presented using frequency tables by SOC and PT.

Previous medication and concomitant medication will be coded using the Anatomical Therapeutic Chemical Classification (ATC) dictionary. Frequency tables will be compiled based on the coding for the medication.

8.1.6 **Missing Data**

Missing efficacy data will not be replaced in general.

If a laboratory reports concentrations as unquantifiable (too low), the value will be set to 0. Values for samples that are not technically evaluable will be set to missing.

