8.1.11 Software used for Statistical Analysis

The SAS® software version 9.2 (SAS® Institute) or higher will be used for the statistical analysis and for the reporting of this study. PK/PD analyses will be performed with Phoenix® WinNonlin® Version 6.3 or higher (Certara L.P).

8.1.12 **Determination of Sample Size**

Initially, since no confirmatory analyses were planned, no sample size calculations were performed. A total of 24 participants was deemed sufficient for 1 treatment group to obtain at least 20 evaluable participants (Day 168 visit completed).

Subsequently the Sponsor undertook a formal sample size calculation so that the Group 2 data could be used to support the dose selection for future Phase 3 clinical trials.

A sample size of 60 has been chosen on clinical grounds. This number gives good power to detect a minimum proportion of 90% subjects achieving castration with central lab serum T <0.5 ng/mL or 1.73 nmol/L at Day 28 from the per protocol population. It is based on the null hypothesis that the true response rate is 74.5%, the average response rate in previous Teverelix trials not achieving 90% response rate. This is tested using a two-sided test with a 5% alpha level against the alternative hypothesis that the response rate is 90%, the minimally clinically relevant response rate. Based on this, fifty participants give power of 80%. Assuming a dropout rate of 16%, sixty patients are recommended.

Sixty patients will ensure acceptable precision for justification for further analysis of this regimen in Phase 3. A true 90% response rate in this instance would give a confidence interval of (79,96) and if 10 subjects drop out, and interval of (78,97). A true 95% response rate with 60 participants would give a confidence interval of (86,99) and if 10 subjects drop out, an interval of (85,99).

8.2 **Data Management**

Data management will be performed using Oracle Clinical Version 3.3 or later running on 2 Microsoft Windows NT servers. Details will be defined in the data management manual, which will be signed by the Sponsor and the Clinical Research Organisation (CRO) prior to start of the data entry.

9 Data Handling and Data Quality Assurance

9.1 **Data Management**

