## **4. Study Measures**

This section describes the measures that were collected and/or derived during the study at the time points specified in the Schedule of Assessments (**Error! Reference source not found.**). This includes efficacy, safety, tolerability and subject characteristics data.

The Baseline value for all variables is defined as the last non-missing measurement collected/derived prior to the first study medication administration at Visit 2/Day 0. This includes unscheduled visits.

The change from Baseline value at each post-baseline visit for all variables will be calculated as the difference between the measurement obtained/derived at the specific post-baseline visit, and the Baseline value.

The two dose groups will be analysed separately – the combined results will not be of interest for the analyses. The combined results would not be of interest as Group 2 would only open to recruitment if Group 1 was deemed ineffectual.

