#### **4.2.9 Predictive Effect of Cardiac Biomarkers**

To assess the predictive effect of cardiac biomarkers for new cardiovascular (CV) events, the following parameters will be collected at Stage 1 (Day 0) and Stage 2 (Day 28, Day 42, Day 84, Day 126, Day 168):

- N-terminal pro-B-type natriuretic peptide (NTproBNP)
- D-dimer
- C-reactive protein (CRP)
- high-sensitivity troponin (hsTn)

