**6.9.7 Predictive Effect of Cardiac Biomarkers**

It is planned that the biomarker parameters (N-terminal pro-B-type natriuretic peptide (NTproBNP), D-dimer, C-reactive protein (CRP), high-sensitivity troponin (hsTn)) will include collected and derived quantitative parameters only. The results, changes from the baseline, and percent change from the baseline for each biomarker parameter will be summarized at each visit.

If any qualitative parameters are collected, they will be summarized by absolute counts (n) and percentages (%). Percentages will be based on the number of subjects with data.

All collected biomarker parameters will be listed.

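### Setting unquantifiably low values to 0 conflicts with the percent-change summaries for the cardiac biomarkers, PSA, LH and FSH; the size depends on a share the documents do not give

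*SAP*

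**What the plan says.** SAP 5.3.2.1 (Laboratory Data) states: "If a laboratory reports a concentration as unquantifiable (too low), they will set the value to 0". Protocol 8.1.6 (Missing Data) agrees: "If a laboratory reports concentrations as unquantifiable (too low), the value will be set to 0". The protocol synopsis repeats it.

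For the four cardiac biomarkers, SAP 6.9.7 states: "The results, changes from the baseline, and percent change from the baseline for each biomarker parameter will be summarized at each visit". SAP 4.2.9 schedules them on Day 0 and on Days 28, 42, 84, 126 and 168; Protocol 7.2.2 and 7.2.3 restrict them to Group 2. SAP 6.8.2 items 18, 23 and 27 plan percent change from baseline at each visit for PSA, LH and FSH.

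Under SAP section 4, baseline is "defined as the last non-missing measurement collected/derived prior to the first study medication administration". SAP 5.1.2 says that "all continuous measures will be summarised descriptively, including number of available values, mean, standard deviation (SD), median" and the extremes are reported.

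Neither document says what to do with percent change when baseline is 0, exempts any analyte with a percent-change summary from the zero rule, or gives quantification limits for these analytes or the share of values expected below them.

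**The concern.** Zero is a workable stand-in where the question is whether a value lies under a cut-off, such as T <0.5 ng/mL or LH <1.1 U/L. It does not work in a ratio. As a baseline it is the denominator, so the percent change does not exist. As a later value it forces the largest possible fall.

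Both consequences push the same way. Men who drop out were selected for very low baselines and would tend to rise. Those who remain include artificial scores of -100%. For the cardiac biomarkers, a downward shift makes a rise look smaller, which is the less cautious direction for safety. For LH, FSH and PSA, which treatment is meant to lower, it makes suppression look larger.

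**Working it through.** **Inputs from the documents.** The zero rule (SAP 5.3.2.1, Protocol 8.1.6), the baseline definition (SAP 4), the percent-change summaries (SAP 6.9.7 and 6.8.2), and 60 men planned in Group 2 (Protocol 8.1.12). The plan states no figure on this point, so there is none to reproduce.

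**Does the rule reach PSA, LH and FSH?** In the SAP it sits under Other Endpoints. Protocol 8.1.6 places it directly after the sentence on missing efficacy data, with no restriction by analyte. The natural reading is that it applies to them.

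**Arithmetic.** The SAP gives no formula, so the standard one is assumed: percent change = 100 × (later − baseline) / baseline.

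- Baseline 0: division by zero, undefined for any later value.
- Quantifiable baseline, later value 0: 100 × (0 − b)/b = −100% for every b. With the limit at 1 unit, a baseline of 1.1 and a true later value just under 1 is a fall of about 9% (0.1/1.1), but scores −100%.

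**Size, under assumptions.** Take a log-normal marker with log-SD 0.7 between men and 0.3 within men. The log-ratio of two visits then has variance 0.3² + 0.3² = 0.18. With no true change, the fully observed median is 0% and the mean is 100 × (exp(0.18/2) − 1) = +9.4%. With a true rise of 20%, the median is +20% and the mean is 100 × (1.2 × exp(0.09) − 1) = +31.3%. The simulated zero-rule results are:

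| Baselines below limit | No percent change, of 60 men | Median, no true change | Mean, no true change | Median, true +20% |
|---|---|---|---|---|
| 2% | about 1 | −0.6% | – | – |
| 10% | 6 | −2.3% | about +4% | – |
| 20% | 12 | about −4% | about 0% | +15.2% |
| 40% | 24 | −7.6% | about −8% | about +11% |

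Dashes mark cells for which no figure is quoted here. At 20% with no true change, about 8% of the men still in the summary score −100%, which is about 4 of 48.

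**Second set of assumptions.** Log-SD 0.8 or 1.2; correlation 0.6 or 0.8; true ratio 0.8, 1.0 or 1.25; 5%, 10%, 20% or 40% below the limit: 2 × 2 × 3 × 4 = 48 settings. The zero-rule mean and median were below the fully observed values in all 48.

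**Which effect does the work?** At log-SD 0.8, correlation 0.8, no true change and 20% below the limit:

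- Mean: +13.6% in all men, +6.8% in the retained men with true values, +1.8% under the zero rule. Selection accounts for 6.8 points and the −100% scores for 5.0.
- Median: about 0%, −5.4% and −5.5%. Nearly all of the shift is selection.

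**The case against.** Four points on the other side have force.

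1. **The shift is conditional.** Without limits or expected shares, nobody can say that it will occur. At 1% or 2% below the limit the no-effect median moves by only 0.3 or 0.6 points, and the four cardiac assays need not share one figure. This stands.
2. **The men are not lost.** SAP 6.9.7 also summarises results and absolute change and lists all biomarker values, and the reported number of available values would reveal the drop-out. Under the first model with a true +20% rise and 20% below the limit, mean absolute change is 0.287 under the zero rule against 0.266 fully observed (marker units with median 1), so that table does not hide the rise. This also stands, though with 40% below the limit the median absolute change falls to 0.
3. **A rise still shows in percent change.** With a true +20% and 20% below the limit, the zero-rule mean is about +23%. That is true, but the fully observed mean is +31.3%.
4. **The table carries no decision.** It is descriptive and single-arm, and no biomarker decision rule is stated.

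A reader might infer that the plan removes every man with a low baseline, or conceals the trial's cardiac safety signal. The documents support neither. Only an unquantifiable baseline is undefined. The biomarkers' stated purpose is to predict new cardiovascular events, and adverse events, triplicate ECGs with QTcF thresholds and Holter monitoring also cover cardiac safety.

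**Conclusion.** The conflict is real: a stated substitution rule meets a stated summary that it cannot serve. Once any values fall below the limit, percent change is undefined for some men or exactly −100% for others, and the summary shifts downward.

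The size is not determinable from the documents. Under the first model the no-effect median runs from about −0.6% at 2% below the limit to −7.6% at 40%; if all values are quantifiable, nothing changes. These figures rest on assumed spreads and the standard formula. They were not fitted to PSA, LH or FSH, where a real fall is expected and the share below the limit may change greatly after dosing.

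The primary endpoint and the other threshold endpoints are not touched by this percent-change problem. This is a cheap improvement, not a flaw that undermines the trial's conclusions.

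**What to change.** **SAP 5.3.2.1.** Keep zero for threshold endpoints, and leave it unchanged for routine safety laboratory values so that they are not left without a rule. For every percent-change or ratio summary (NTproBNP, D-dimer, CRP, hsTn, PSA, LH, FSH), use a stated non-zero substitute such as LLOQ/2.

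**SAP 6.9.7 and 6.8.2 items 18, 23 and 27.** Add the geometric mean ratio to baseline with 95% CI, and the number below the limit at each visit. The CI must be named in 6.9.7, because SAP 5.1.2 reserves it for efficacy measures.

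The ratio matters as much as the substitute. Under the first model with LLOQ/2, the geometric mean change is 0.0% when the truth is 0, and +21.3% (20% below) or +19.6% (40% below) when the truth is +20%. Substitution alone does not rescue arithmetic percent change. At log-SD 0.8, correlation 0.8, true ratio 1.25 and 40% below, the LLOQ/2 median is +2.8% against +25.1% fully observed, and the mean is +47.9% against +42.1%.

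**Data transfer.** The SAP has the laboratory insert the 0. Ask it to send the `<LLOQ` flag and the limit; for PSA, the limit of whichever assay gave the reported value.

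**SAP 7.1.** Record the departure from Protocol 8.1.6.

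**Cost.** SAP wording, a laboratory data field and slightly more programming. LLOQ/2 is a convention; where most values at a visit are below the limit it largely determines the ratio, so the counts must be shown beside it.
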